**Table 2. Sites for DECAD Recruitment\***

Site	Number of sites	# of Physician s	Women ≥70 years old with AD	Race and Ethnicity for population with AD
Eskenazi Health Aging Brain Care Program	1	5	1,383	White 42% African American 51% Other or unknown 7% Hispanic 2%
Indiana University Alzheimer Disease Center	1	NA	43	White 67.5% African American 32.5%
Indiana University Health Department of Neurology	1	3	TBD	TBD
Alzheimer's Association- Greater Indiana Chapter	5-10	NA	TBD	TBD
IU Health PC		179	2,026	White 75.6% African American 22.4%

- Caregivers will be age 18 and older and an unpaid, informal caregiver for the patient either self-identified, identified by the patient, or identified by the patient's medical team.
- See Table 1 for patient and caregiver inclusion and exclusion criteria.

*Recruitment Sites (as of 11/30/2021):*

- Aging Brain Care Program at Eskenazi Health
- Indiana University Alzheimer Disease Center (research registry)
- Indiana University Health Department of Neurology
- Indiana University Health Department of Psychiatry (Drs. [name] and [name])
- Alzheimer's Association- Greater Indiana Chapter (Support Group members)
- Indiana University Health Primary Care Practices in central Indiana
- Eskenazi Health Primary Care Practices in central Indiana
- Beth Israel Deaconess Medical Center, Boston, Massachusetts
- Parkview Health, Fort Wayne, Indiana
- CICOA Aging and In-Home Services, central Indiana
- LifeStream Services, eastern Indiana
- Thrive Alliance, southern central Indiana
- SWIRCA & More, southwest Indiana

	14 PC practices			Other or unknown 2% Hispanic 0.9%
BIDMC	7 sites	90	1600	White- 64% Black- 23% Asian- 4% Hispanic -5%
Parkview Health	TBD	TBD	TBD	TBD
CICOA Aging and In-Home Services	NA	NA	988	TBD
LifeStream Services	NA	NA	200	TBD
Thrive Alliance	NA	NA	40	TBD
SWIRCA & More	NA	NA	90	TBD
Total	34	277	6280	

\*Data as of March 2017 besides BIDMC, Parkview Health, CICOA, LifeStream, Thrive Alliance, SWIRCA & More

*Primary outcome:* Caregiver decisional conflict at post-index visit (T3)

*Secondary outcome (caregiver):* Caregiver decision-making self-efficacy at post-index visit (T3)

*Secondary outcome (patient):* Utilization of mammograms at 15 (T4) and 24 months post-index visit (T5).

Table 3. Measures							
Outcomes	Construct/Core Attributes	Outcome measure(s)	Name of Measure citation	Description	Scoring	When	Source
Primary outcome	Feel Informed Values clarification	Decisional Conflict	Decision Conflict Scale	16-items on a 1-5 Likert scale. Measures uncertainty around a decision, whether	Scores range 0-100; Lower	T1 T3	Caregiver reported

				one feels informed, clear about their personal values, and supported in their decision-making.	scores indicate less conflict.		
Secondary outcomes	Belief in ability to make and participate in shared decision making	Decision-making self-efficacy	Decision Self-Efficacy Scale (DSE)	11-items on a 5-point Likert scale. Measures of self-confidence or belief in one's ability to make decisions	Low, medium, high decision self-efficacy. Scores range 0-100	T1 T3	Caregiver reported
		Receipt of screening	DECAD Created	Review primary care notes, radiology reports, and documentation on screening/preventive care; caregiver report	Yes or no determination	T4 T5	Pt EMR; Caregiver reported
	Involvement in the decision	Caregiver role in decision-making	Adapted from the Control Preferences Scale	4-items to assess preferences for and involvement in making decisions on their own or sharing responsibility with the pt or doctor.	Active vs. passive/shared with doctor (since aim of decision aids is to help dyads be more active in decision-making)	T3	Caregiver reported
		Patient role in decision-making	Adapted from the Control Preferences Scale	2-items to assess involvement in making decisions on their own or sharing responsibility with their family or doctor.	Active vs. passive/shared with doctor (since aim of decision aids is to help dyads be more active in decision-making)	T3	Patient reported
Other measures		Socio-demographics	DECAD Created	32 item questionnaire to measure items such as relationship to the patient, frequency and type of contact with the patient, geographic distance from the patient, education level, annual income, self-reported health status, etc.	Co-variates	T1	Caregiver reported
	Does severity of the patient's cog and functional impairment impact caregiver decision making	Severity of patient's cognitive impairment	Dementia Severity Rating Scale (DSRS)	12-item questionnaire for caregivers to assess severity of AD in 12 major functional and cognitive domains.	Score ranges from 0 (mild) to 54 (severe).	T1	Caregiver reported
			Caregiver Appraisal of Function and Upset (CAFU)	15-item questionnaire for caregivers to measure ADLs and iADLs impairment and how much those impairments upset or burden the caregiver		T1	Caregiver reported
		Intention for the patient to be screened	DECAD Created	3-items total. Two on a 5-point scale to assess propensity to get screened. One to ask how many more mammograms they think the patient will get.	Yes vs. those who are unsure vs. No screening; We will look at the scores continuously and categorize scores as 1-2(no), 3 (unsure), or 4-5 (yes).	T1 T3	Caregiver and Patient reported

		Breast Cancer and Alzheimer's disease Knowledge	DECAD Created	16-items (6 multiple choice and 10 true/false); 13 were adapted from other studies and 3 were developed based on the decision aid.	Sum of correct answers	T1 T3	Caregiver reported
		Burden of screening on the patient	DECAD Created	Review patient's EMR for additional diagnostic procedures due to mammogram follow-up; false-positive results, identification of an abnormality on screening exam but further work-up declined, identification of a clinically unimportant cancer; documentation of depressive symptoms, anxiety, or pain related to the experience of getting a mammogram and not a general measure to be assessed independent of that event	Yes or no Characterization if yes	T4 T5 (quarterly for DSBM )	Pt EMR review;
		Burden of screening on the caregiver	DECAD Created	5 items on a 5-point Likert scale. Assess perceptions about the burden of mammography for the patient & Semi-structured questions about patient's mammogram experience and perceived burden of screening.	Sum of scores	T4	Caregiver reported
	Values, Attitudes, Norms, and Experiences		DECAD created	15 items total. 5 items on a 10 point scale re: values; 3 items on a 7 point scale on attitudes; and 3 items on a 5 point scale re: perceived norms; and 4-items on a 5 point scale re: experience with mammograms	descriptive	T1 T3	Caregiver and Patient reported
		Health literacy		A 4-item health literacy assessment with values of 0-5 based on possible responses to each of the questions. 	Higher scores being higher health literacy.	T1	Caregiver reported
		Numeracy		A 3-item assessment of numeracy skills	Higher scores being higher health literacy.	T1	Caregiver reported
	Mammogram discussion with the Patient's provider			8-items that assess if a discussion about mammograms took place and the content of those discussions.	Descriptive	T3	
Process measure		Acceptability of the decision aid	DECAD Created	3-items on a yes/no scale and 6-items on a 5-point Likert scale to measure caregivers' and patients' perceptions about the length, clarity, helpfulness and willingness to recommend decision aid. Also, the number of times they reviewed it, how many pages they read, how long it took them to read it, how they would prefer to receive it if not part of a study.	Sum of scores	T3	Patient reported
Process measure		Acceptability of the decision aid	DECAD Created	20-items on a 5-point Likert scale and 8 yes/no questions to measure	Sum of scores	T3	Caregiver reported

				
caregivers' and patients' perceptions about the length, clarity, helpfulness and willingness to recommend decision aid.
 
Also, the number of times they reviewed it, how many pages they read, how long it took them to read it, how they would prefer to receive it if not part of a study.
			
--	--	--	--	---	--	--	--

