**Decisions about Cancer Screening in Alzheimer's Disease**  
**(DECAD)**

**PROTOCOL**  
**4.28.2022**

**BACKGROUND AND STUDY AIMS**

The incidence of both Alzheimer's disease and related dementias (AD) and of breast cancer increases with age; thus, many older women with AD are faced with questions about breast cancer screening. Having AD can impact a women's ability to participate in her medical decision-making about breast cancer screening. As a result, AD family caregivers (hereafter referred to as caregivers) are frequently involved in making decisions about mammography. Each year over 800,000 women with AD receive screening mammography. Caregivers cite decision-making and procedures related to mammograms as particularly stressful and there is a lack of data that mammography screening helps women with AD live longer or better.

The average life expectancy of older women with AD is <10 years. Current guidelines recommend not screening women with a life expectancy of <10 years. The rationale is that these women will not live long enough to experience the life prolonging benefits of mammography screening. Instead, screening these women can put them at risk for physical and psychological harm as a result of over diagnosis, overtreatment, additional tests due to false positives, and the identification of clinically unimportant cancer. Conversely, while mammography screening may not help older women with AD live longer, it may help find breast cancers earlier when they are easier to treat. Therefore, it is important that women with AD and their caregivers have information to make an informed decision about screening. The goal of our project is to test if an evidence-based decision aid for caregivers can improve the quality of decision-making about mammography in older women with AD.

A decision aid for AD caregivers about mammography could improve the quality of medical decision-making, by informing caregivers about the risks, benefits, and their choices. No decision aids exist to support AD caregivers with decisions about mammography despite the frequency that caregivers are approached with this decision. The DECAD Study will test if a decision aid can support AD caregivers and patients in making decisions about breast cancer screening by improving markers of decision quality. The study aims are:

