**Primary Aim: To examine the effect of a mammography screening decision aid intervention for older women with AD on markers of decision quality among caregivers.**

Hypothesis: Caregivers of patients who receive the decision aid will have lower levels of decisional conflict (primary outcome) and higher levels of decision-making self-efficacy (secondary outcome) about breast cancer screening in older women with AD, compared to the control group.

**Secondary Aim: To examine the effect of a mammography screening decision aid intervention for caregivers on the utilization of mammograms in older women with AD.**

Hypothesis: Women with AD who are randomized to receive the decision aid will receive less mammography screening at 15 and 24 months after the intervention, compared to the control group.

**Exploratory Aim: To identify the factors that are associated with impact of a decision aid intervention on mammography screening cessation in older women with AD.**

Exploratory Hypothesis: Among the dyads randomized to receive the decision aid, caregivers of patients with more severe cognitive impairment, greater co-morbidities, or older age will experience a greater reduction in frequency of mammograms in the 15 and 24 months following the intervention.

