**Collecting**- All adverse events, unanticipated problems and potential risks will be monitored and collected ongoing and throughout the study by the DECAD research assistants and research manager. Monitoring events related to an increased risk that a malignancy of the breast may go undetected or any complications, distress, or pain that arise from receiving a mammogram or as a result of follow-up procedures after a mammogram will be done via electronic medical record reviews of study patients’ primary care encounter notes, radiology reports, and other documentation on screening/preventive care for breast cancer and from caregiver reports. Events related to any patient and caregiver loss of privacy or confidentiality or fatigue, frustration or distress related to completing the intervention or the outcome questionnaires will be assessed by the research manager via monitoring of the delivery of the study protocols and procedures and by patient and caregiver reports.

For all participants, adverse events will be collected starting at enrollment and continue until after the participant has completed the study. If an adverse event occurs, it will be documented on the NIA adverse event and serious adverse event forms found at <https://www.nia.nih.gov/research/dgca/clinical-research-study-investigators-toolbox/adverse-events>. Unanticipated problems, that do not meet the definition of an adverse event, will be documented in a DECAD study log that will be stored in a secure electronic folder behind the IU fire wall. Details in the log may include participant study ID, date that the problem was reported or discovered by the study, a description of the problem, and a corrective plan and measures to prevent reoccurrence.

**Measurement and Reporting of Adverse Events**- Adverse events associated with reviewing a paper-based decision aid on mammography are infrequent. Therefore, adverse event rates are expected to vary little between the treatment and control groups. Adverse events will be monitored by the research manager on an ongoing basis. All adverse events and unanticipated problems will be reported to the study PI within 24 hours. We plan to present unblinded adverse events data to the DSMB when requested and at scheduled meetings. The NIA adverse event form will be used by the study staff to report all adverse events caused by the intervention.

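### The record review of screening burden counts only events that follow a mammogram, and the named risk of an undetected breast cancer is tied to no specific record finding

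*Combined protocol and SAP*

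**What the plan says.** The Table 3 row Burden of screening on the patient is a medical-record review, scored yes or no with a description if yes. It is done at T4 and T5 and is also marked "quarterly for DSBM" (evidently the DSMB). Its items are "additional diagnostic procedures due to mammogram follow-up; false-positive results, identification of an abnormality on screening exam but further work-up declined", followed by "identification of a clinically unimportant cancer; documentation of depressive symptoms, anxiety, or pain related to the experience of getting a mammogram". The row adds that those symptoms are not to be assessed apart from the mammogram.

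Under Adverse Events Reporting, the Collecting paragraph takes up the opposite risk: "Monitoring events related to an increased risk that a malignancy of the breast may go undetected". The sources are "electronic medical record reviews of study patients’ primary care encounter notes, radiology reports, and other documentation on screening/preventive care for breast cancer", plus caregiver reports. Adverse events are collected for all participants from enrolment, and the definition of a non-serious event is broad enough to include a disease arising during participation. Unblinded adverse-event data go to the DSMB, with quarterly summaries. The Measurement and Reporting paragraph, however, describes the NIA form as the one for reporting events that the intervention caused. It also says that "adverse event rates are expected to vary little between the treatment and control groups".

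The secondary hypothesis is that women in the decision-aid arm "will receive less mammography screening at 15 and 24 months after the intervention". The section refers to an attached DSMP and DSMB charter, which are not part of the supplied text.

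**The concern.** The trial hypothesises that the aid will reduce mammography. Less mammography has two kinds of consequence: fewer harms from being screened, and possibly some cancers found later and by other routes. The Background acknowledges both, since it says screening may find cancers when they are easier to treat. The itemised record review covers only the first kind. A cancer that presents as a lump in a woman who stopped screening fits none of its items.

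For the second kind, the plan names a risk and some sources, but no finding for the abstractor to record. If staff apply the causal wording attached to the adverse-event form, they must decide whether a cancer diagnosed months later was caused by a paper decision aid, and they could easily decide that it was not.

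The item on clinically unimportant cancer adds a further problem. Whether a cancer would ever have mattered to one woman cannot be settled yes or no from at most 24 months of her notes. A cancer given that label is then counted as a burden of screening.

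At stake is the completeness of the safety account given to the DSMB and in the final report. The primary outcome, caregiver decisional conflict, is not affected.

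**Working it through.** **1. Number per arm.** The Statistical Power section needs 202 completers per group and allows 5% missing: 202 / 0.95 = 212.6, so 213 per group. This reproduces the stated figure and is used below.

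**2. How the burden count moves with uptake.** Let u be the proportion screened and h the probability of a listed event per screened woman. Expected events per arm = 213 × u × h. If h is the same in both arms, the ratio of counts equals the ratio of uptakes. Uptake ratios of 0.9, 0.7 and 0.5 give 10%, 30% and 50% fewer counted events, whatever the value of h.

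The documents give neither u nor h. As an illustration, assume control uptake of 50%, decision-aid uptake of 35% to 40%, and h = 20%:

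- Control: 213 × 0.50 × 0.20 = 21.3
- Decision aid at 40%: 213 × 0.40 × 0.20 = 17.0
- Decision aid at 35%: 213 × 0.35 × 0.20 = 14.9

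Across a wider range (control uptake 30% to 70%, h = 10%), controls have 6.4 to 14.9 events. The decision-aid arm has 4.5 to 10.4 at a ratio of 0.7.

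These gaps are within chance for a trial of this size. For 10% against 7%, the pooled proportion is 0.085 and the standard error is √(0.085 × 0.915 × 2/213) = 0.0270, so z = 0.03/0.0270 = 1.11 and p = 0.27. For 10% against 8%, the standard error is 0.0277, z = 0.72 and p = 0.47. The point is the direction built into the item list, not a significant difference.

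**3. How many cancers could be listed.** The documents give no incidence. Assume 2 to 6 per 1,000 woman-years over 24 months, ignoring deaths and losses:

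- 213 × 2 × 0.002 = 0.85 per arm
- 213 × 2 × 0.006 = 2.56 per arm

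With 0 cases among 213, the one-sided 95% upper bound is 1 − 0.05^(1/213) = 1.4%.

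**4. Could a test be done?** Power to see a doubling with 213 per arm (two-sided 0.05, normal approximation):

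| Assumed 24-month control risk | Expected control cases | Power for a doubling |
|---|---|---|
| 0.4% | 0.9 | 8% |
| 0.8% | 1.7 | 11% |
| 1.6% | 3.4 | 19% |

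The last row corresponds to 8 per 1,000 woman-years, above the range in step 3. No realistic test is available.

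**5. Where a symptomatic cancer in an unscreened woman would be recorded.**

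| Place in the plan | Would it be recorded? |
|---|---|
| Table 3, Burden of screening on the patient | No; every item follows a mammogram |
| Table 3, Receipt of screening | No; records only whether she was screened |
| Adverse Events Reporting, definitions and collection for all participants | It could be; the definition is broad enough |
| Adverse Events Reporting, sentence on the NIA form | Uncertain; depends on a judgement of cause |
| DSMP and DSMB charter | Not known; not supplied |

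None of the supplied rows or paragraphs asks for mode of detection or stage.

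**The case against.** The strongest reply is that a route already exists. A breast cancer diagnosed later is a disease arising during participation, and if it leads to hospitalisation or death it is serious. Adverse events are collected for every participant and summarised to the DSMB. This stands: a reader might infer that a missed cancer has no countable event anywhere in the trial, and the documents do not support that. They also refer to a DSMP that evidently lists anticipated events and may define this one. What remains is that the supplied text does not say which finding counts, and the sentence on the form brings in a causal filter.

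Second, the Table 3 row is titled as burden of screening, so listing consequences of screening is its purpose, and it is not the only record review in the table. Both are correct. But among the Table 3 rows it is the one marked for quarterly DSMB review, and it has no defined counterpart.

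Third, a reader might infer that the trial's harm comparison is biased towards the decision aid. The documents plan no between-arm test of harms, and fewer screening harms after less screening would be a genuine effect. The defect is only that it would be shown without its counterpart.

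Fourth, the sentence that "adverse event rates are expected to vary little between the treatment and control groups" follows from a remark about reviewing a paper aid. Read that way it does not contradict the secondary hypothesis. It needs a stated scope, not deletion.

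**Conclusion.** The concern holds as a gap in defined capture. The itemised burden review moves one for one with uptake at equal harm per screened woman: 30% fewer counted events at an uptake ratio of 0.7. The named opposing risk has no specific record finding in the supplied text, and its capture through adverse-event reporting is uncertain. The item on clinically unimportant cancer cannot be answered reliably for an individual within the follow-up.

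The event counts rest on assumed uptake, harm and incidence rates; the proportionality does not depend on the values chosen. With about 1 to 3 cancers per arm, nothing here could be tested. A reader might also take few or no recorded cancers at 24 months as evidence that screening less is safe. The follow-up cannot support that: zero cases in an arm would still be compatible with a risk of 1.4%, and the rationale in the Background, that "these women will not live long enough to experience the life prolonging benefits of mammography screening", concerns a horizon of about 10 years. The change should be made, but it does not touch the primary analysis. If the DSMP already defines and lists these events, a cross-reference closes that part of the point.

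**What to change.** - In the existing T4, T5 and quarterly abstraction, record for every randomised woman, screened or not and without a judgement of cause: any breast cancer diagnosis, its date, mode of detection (screening, symptom, incidental), stage, and any breast work-up prompted by symptoms.
- Use these facts in place of the item on clinically unimportant cancer.
- List them by arm, per woman randomised, beside the screening-burden events in DSMB reports and the final report. If the DSMP or charter already does this, cite it in Table 3.
- Reconcile the sentence on the adverse-event form with the collection of all adverse events.
- Limit the sentence on similar event rates to events from reviewing the paper materials.
- State that the cancer listing is descriptive and that 24 months cannot show that reduced screening leaves cancer outcomes unchanged.

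The cost is a few more fields on a form already applied to the same records at the same times, some protocol wording, and a stated limit on the safety conclusion.

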### *Intervention Description and Timing of Measures*

Although participants may be recruited from specialty memory care or AD clinics, the intervention will be delivered in the patient's primary care setting (e.g. the usual setting for discussions about mammography).

[figure not shown]
